## 8.4 DESIGN: Briefly describe the study design (e.g., observational, interventional, randomized, placebo-controlled, blinded, cross-over, cross-sectional, longitudinal, pharmacokinetic, etc.):

We will recruit 640 rural dementia caregiver adults through 19 community organizations (serving rural communities in 17 states to implement a randomized, attention controlled clinical trial. Caregivers will be randomized to receive the online intervention (workshop) group or attention control group. The online workshops will be facilitated by trained caregivers who will lead workshops. We will assess both primary and secondary outcomes at baseline, 1.5 months (post intervention), 6 and 12 months, with the main intervention group comparison being at 12 months. Interested control group caregivers also will be offered the workshop after the trial is completed.

Using mixed methods approach we will identify implementation characteristics pertinent to caregivers, identify patterns of experience across all workshop participants via analysis of implementation questions embedded in trial surveys administered to all participants. To more deeply understand these experiences, we will interview a sample of 60 caregivers—15 per US region (West, Midwest, Northeast, South).

To determine implementation characteristics pertinent to community organizations, we will collect data from our partner community organizations on experiences of barriers and facilitators. Analyses will compare and contrast characteristics within and between organizations. Findings will

identify essential elements of workshop implementation that should be incorporated into future implementation efforts. Findings on effective and ineffective strategies will inform the implementation of other online programs for rural, caregiver, and Alzheimer's disease populations.

**8.5 BACKGROUND AND SIGNIFICANCE: Briefly provide the background and significance of this study (e.g. why is this study needed) (space limit: one half page):**

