b. **Attention control group.** Participants will receive written materials on dementia and caregiver resources and two brief phone calls of 15-30 minutes apiece by research staff. Caregivers in the attention control group will be offered the online workshop after the 12 month trial is completed if they so desire. The written materials and phone call guides are still under development and will be submitted to the IRB for review as a modification request.

**For control group fidelity purposes.** Phone calls will be recorded. [name] and the research coordinator will evaluate recordings using a fidelity assessment instrument. Staff who stray from the phone call protocol will receive immediate remedial training. If an RA strays from the protocol again, he/she will be removed from making phone calls. At the outset of the trial, fidelity assessment will occur approximately every 4-5 calls to assure fidelity patterns are quickly established and reinforced. Subsequent checks will occur every 10-12 calls.

5. **Assessments:** Data will be collected at baseline, 1.5 months (post intervention), 6 months, and 12 months. Data will be collected through online surveys completed by caregivers and conducted at baseline, post-intervention (1.5 months), and 6, and 12 months using the secure REDCap application. Assessments are expected to be 20 minutes each. Participants will be given the option to complete surveys by mail or phone interview.

a. **Baseline** questions will ask about caregiver and PWD demographic information (e.g., age, gender, race/ethnicity, education); caregiving relationship to PWD (e.g., spouse, child), and resources participants are accessing (e.g., paid in-home care). Baseline questions also will identify caregiver and partner chronic conditions (e.g., using the Charlson comorbidity index), partner need for assistance with ADLs and IADLs, and dementia characteristics (e.g., diagnosis, length of diagnosis, degree of impairment, presence of behavioral symptoms). Caregiver (CG) stress level (Stress visual numeric scale), CG depression symptoms (PHQ-8 score), Self-efficacy (Revised Scale for Caregiver Self-efficacy), Burden (Zarit Burden Inventory), Strain (Caregiver Strain Index), Global health score, and Healthcare utilization items.

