**Aim 1 Instrument.**

Descriptive variables.

- Baseline questions will ask about caregiver and patient with dementia (PWD) demographic information (e.g., age, gender, race/ethnicity, education);
- caregiving relationship to PWD (e.g., spouse, child),
- resources participants are accessing (e.g., paid in-home care).
- caregiver and PWD chronic conditions (e.g., using the Charlson comorbidity index),
- PWD need for assistance with Activities of Daily Living (ADLs) and Instrumental Activities of Daily Living (IADLs),
- PWD dementia characteristics (e.g., diagnosis, length of diagnosis, degree of impairment, presence of behavioral symptoms).

Primary outcomes.

- Caregivers describe high personal stress as one of the most challenging aspects of being a caregiver. We will use a single-item visual numeric scale (range 1-10) developed by our team. Visual numeric scales [VNS] have been shown to correlate well [ $r = .72$ ] with same-worded visual analogue scales [VAS] and generate higher completion rates.
- We will measure the co-primary outcome of caregiver depression symptoms with an 8-item modified and validated version of the PHQ-9.

Secondary outcomes.

- Self-efficacy will be measured with the 15-item Caregiver Self-Efficacy scale.
- Caregiving burden will be assessed with the 12-item short form of the Zarit Burden Inventory.
- The modified 13-item Caregiver Strain Index will measure caregiver strain.
- Single-item caregiver-reported data will be collected on caregiver and PWD global health, hospitalizations, and emergency room visits.
- We will use the National Health and Nutrition Survey question on global health.
- We will measure healthcare utilization using single-item questions on hospitalizations and emergency room visits that have been demonstrated in multiple studies to be reliable within the 6-month recall time frame we are using, including among dementia caregivers.

**For intervention arm only:** We will embed implementation questions administered to all intervention group caregivers at baseline and months 1.5, 6, and 12. Questions will ask about various aspects (e.g., how heard about trial, reasons for participation, ease of/barriers to logging into workshop and performing online activities, whether completed the workshop and, if not, why not; whether workshop experiences have continued to influence their self-care or caregiving practices or own/partner's health).

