**8.26 STATISTICAL METHODS: Briefly summarize the methods and types of analyses that will be performed:**

**Aim 1 Data Analysis Methods.**

**Descriptive analyses.** Caregiver and caregiver-reported partner socio-demographic characteristics, chronic conditions, and health utilization outcomes will be summarized as means ( $\pm$ SD), frequencies, percentages, and 95% confidence intervals at baseline and 1.5, 6, and 12 months. The distributions of covariates at baseline will be checked for balance between the two groups with histograms and/or boxplots.

**Primary analyses.** Primary analyses will compare caregiver stress (stress score) and depression symptoms (PHQ-8 score) between intervention and control groups over time with respective linear mixed effects models. Linear mixed effects models use all available observations in the data, assume data are missing at random, and provide an intention-to-treat analysis. Models will include group, time, and (group\*time) interaction terms as fixed effects and community organizations and subjects as random effects to account for the correlation within organizations and subjects due to measurements over time. Covariates with imbalanced distributions between the two groups will also be included in the models to control for potential confounding. The (group\*time) interaction term will be used to evaluate if the two groups differ in outcomes over time. The study is powered to allow 30% loss to follow up. To assess for potential differential withdrawal between groups, comparisons of withdrawal rates and time to withdrawal will be performed. Models based on a potential outcome framework will be used to assess treatment effect while accounting for noncompliance and missing data and to examine potential treatment mechanisms/pathways via intermediate variables (such as social support, self-efficacy, caregiving skills). Multiple imputation based on reasonable assumptions on mechanisms of missing data will be used to perform sensitivity analyses.

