**Secondary analyses.** Secondary analyses will use (generalized) linear mixed effect models similar to the primary mixed effect models for continuous, categorical, and count secondary outcomes. Treatment effects in subgroups (e.g. by sex) of our interest will be evaluated using (generalized) linear mixed effect models with corresponding interactions of group, time and sex while controlling for false discovery rate. We expect a small and balanced recall error between the two groups but if recall error is unbalanced, measurement error models will be considered for treatment evaluation. We will examine loss to follow-up by comparing caregivers lost to follow-up to those who complete the study.

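### Hospitalization and ER-visit counts: testing group*time divides the follow-up rate ratio by a noisy baseline ratio; using the baseline count as a covariate keeps the 12-month question and gives a more precise test

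*Combined protocol and SAP*

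**What the plan says.** All references are to the Combined protocol and SAP unless stated.

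- **Outcomes (8.12 Instruments, secondary outcomes).** "Single-item caregiver-reported data will be collected on caregiver and PWD global health, hospitalizations, and emergency room visits". The same list adds: "We will measure healthcare utilization using single-item questions on hospitalizations and emergency room visits". This gives four utilization outcomes: two event types, each for the caregiver and the person with dementia. The items are described as "reliable within the 6-month recall time frame we are using, including among dementia caregivers".
- **Timing (8.10, Assessments).** The baseline survey ends with "Strain (Caregiver Strain Index), Global health score, and Healthcare utilization items", and the utilization items recur at 1.5, 6 and 12 months.
- **Model (8.26, Secondary analyses).** "Secondary analyses will use (generalized) linear mixed effect models similar to the primary mixed effect models for continuous, categorical, and count secondary outcomes".
- **Test (8.26, Primary analyses).** The models have group, time and group*time "interaction terms as fixed effects and community organizations and subjects as random effects". The "interaction term will be used to evaluate if the two groups differ in outcomes over time".
- **Main comparison (8.4 Design).** "We will assess both primary and secondary outcomes at baseline, 1.5 months (post intervention), 6 and 12 months, with the main intervention group comparison being"; the time point named there is month 12.

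Section 8.26 states no other contrast for counts and names neither a baseline covariate nor a total-events analysis. The Protocol document (the August 2019 power memo) selects varying randomization ratios and says the ratio will enter the analysis model as a categorical term.

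**The concern.** On the log scale, a group*time term for a count is a ratio of ratios: the between-arm rate ratio at follow-up divided by the between-arm rate ratio at baseline. Randomization already sets the baseline ratio to 1 in expectation. Estimating it freely and dividing by it removes no bias. It adds the Poisson noise of a sparse baseline count, in exchange for removing stable differences between caregivers. A covariate removes those stable differences at lower cost.

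At stake is the precision of the utilization results. If the group*time term is reported as planned, the confidence interval for each of the four outcomes is wider than the data require, and a moderate effect in either direction is more easily read as no effect.

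**Working it through.** **The plan's own figure.** Section 10.3 gives power only for PHQ-8: 224 per group, effect size 0.265, two-sided 0.05. The noncentrality is 0.265 × √(224/2) = 2.804, and Φ(2.804 − 1.960) = 0.80, as stated. There is no corresponding figure for utilization.

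**Inputs.** From the documents: n = 224 per arm, utilization measured at baseline and follow-up, 6-month recall. Assumed, because the documents are silent: mean events per 6-month window *m*, between-caregiver (gamma frailty) variance *k*, rate ratio RR, and frailty constant over time. The organization effect is left out, as is the 1.5-month report, because a 6-month look-back there would reach before randomization.

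**Formula.** Take the 12-month log rate ratio minus *b* times the baseline log rate ratio. The variance contributed by each arm is

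[(1/m₁₂ + k) + b²(1/m₀ + k) − 2bk] / n

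- b = 1 is group*time: (1/m₀ + 1/m₁₂)/n.
- The minimum is at b = k/(1/m₀ + k), which is what baseline adjustment, or constraining the arms to be equal at baseline, approximates.
- The excess of b = 1 over the minimum is (1/m₀)² / (1/m₀ + k) / n. It is always positive and is largest for rare events with modest *k*.

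**Worked case: m = 0.2, k = 2, RR = 0.70 (log −0.357).**

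| Analysis | Control | Intervention | Sum/224 | SE | Power |
|---|---|---|---|---|---|
| 12-month group*time | 5 + 5 = 10 | 5 + 7.143 = 12.143 | 0.0989 | 0.314 | 0.21 |
| 12-month, baseline-adjusted | 7 − 4/7 = 6.429 | 9.143 − 4/7 = 8.571 | 0.0670 | 0.259 | 0.28 |
| 0-12-month total, baseline-adjusted | 2.5 + 2 − 4/7 = 3.929 | 3.571 + 2 − 4/7 = 5.000 | 0.0399 | 0.200 | 0.43 |

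The best weight on baseline here is 2/7 = 0.29; group*time forces it to 1. Simulation of the same case gave 0.21 for group*time and 0.44 for the adjusted total.

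**Simulation at m = 0.2, RR = 0.65 in both windows.** Power was 0.24-0.26 for 12-month group*time, 0.34-0.38 for the 12-month count with baseline as covariate, and 0.54-0.64 for the adjusted total. Across the simulated scenarios with *m* 0.1-0.3 and RR 0.65-0.70, the three ranges were about 0.11-0.29, 0.18-0.40 and 0.28-0.64. At the most favourable corner (m = 0.3, k = 1, RR = 0.65) the formula gives 0.38, 0.53 and 0.77. Rejection under the null was about 0.06-0.07.

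**Late effect: RR = 1 in months 0-6, then 0.65, m = 0.2.** The total's rate ratio becomes (0.20 + 0.13)/(0.20 + 0.20) = 0.825, so the log effect shrinks from −0.431 to −0.192. Simulated power is 0.18 for the adjusted total against 0.30 for 12-month group*time. The adjusted 12-month count still beat group*time here.

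**Frequent, strongly person-driven events: m = 0.5, k = 4, RR = 0.70.** By formula, group*time has power 0.43, an unadjusted total 0.38, the adjusted 12-month count 0.49 and the adjusted total 0.66. Dropping the baseline altogether can therefore do worse than group*time; adjusting for it does not.

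**The case against.** A reader might infer that the total count should replace the planned test and would roughly double power. The documents do not support that as a general claim. It needs a similar effect in both halves of the year, and nothing in them says when a utilization effect would appear. Section 8.4 also sets the main comparison at 12 months for secondary outcomes as well as primary ones, so a 0-12-month total answers a different question. This part of the objection stands, and it is why the total belongs in a supporting role.

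A reader might also infer that real effects would be missed because of the test rather than the data. That goes too far. At a rate ratio of 0.85 and rates of 0.15-0.3, simulated power is 0.07-0.11 with group*time and only 0.11-0.19 with the total. The plan makes no power claim for these outcomes.

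Three further points are fair:

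- Section 8.26 is a brief summary, and its word for the secondary models (similar) fixes no contrast for counts. Even so, group*time is the only test it describes.
- Section 8.12 gives no response format for the single items. That they record counts is an inference, supported by 8.26 listing count outcomes.
- The figures use the 1:1 split of 10.3, not the varying ratio. With 320/160 (m = 0.2, variance 2, RR = 0.70), simulated power is 0.22 for group*time and 0.45 for the adjusted total, so the direction is unchanged.

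That differencing also removes stable between-caregiver variation is true, but the formula shows that adjustment does so at lower variance.

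**Conclusion.** The concern holds in a limited form. As described, the test for the utilization counts is less precise than one using the same baseline data as a covariate, and the alternative leaves the 12-month question intact. Under the stated variance model this holds for any event rate and dispersion. In the simulations, baseline adjustment at 12 months beat 12-month group*time in every non-null scenario.

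The size rests on assumed rates, dispersion and rate ratio. In the worked case the variance falls by about a third (0.0989 to 0.0670) and power rises from 0.21 to 0.28. The larger gain from the total depends on an effect present through both windows. These are secondary outcomes, and no choice of test makes them well powered. The point concerns efficiency and pre-specification; it does not challenge the validity of the trial.

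**What to change.** In 8.26, for the four utilization outcomes:

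1. **Main analysis.** Estimate the between-arm rate ratio at follow-up, with the 12-month comparison as the test. Use a negative binomial or robust Poisson mixed model with the baseline count as a covariate, or with the arms constrained equal at baseline. Include the organization effect and the randomization ratio as a categorical term, in line with the Protocol document. Name the standard-error method in advance, since null rejection in simulation was slightly above 0.05.
2. **Supporting analysis, pre-specified.** Compare total events over months 0-12, from the 6-month plus 12-month reports, with the baseline count as covariate and an offset for months reported so that caregivers with one of the two surveys contribute. Leave out the 1.5-month report to avoid double counting.
3. **Group*time for counts.** Keep it as a description of timing only.
4. **Section 8.12.** State that the items record a number of events.

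The cost is SAP wording. No new data or contacts are needed: the utilization items are already in the baseline survey, which 8.10 places before randomization. The trade-off is that the utilization test no longer addresses change from baseline as such.

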**Aim 2 Data Analysis Methods.**

We will use mixed methods and multiple data sources to generate findings. We will identify facilitators and barriers of workshop implementation pertinent to caregivers.

**Data analyses using all intervention caregivers' :** We will embed implementation questions in the web-based trial surveys administered to all intervention group caregivers at baseline and months 1.5, 6, and 12. We will perform descriptive and comparative analyses of the survey-based and platform-derived data to identify notable barriers and facilitators of workshop implementation for intervention group caregivers. For example, we will analyze participation rate by caregiver sub-groups (e.g., region, age, gender, race/ethnicity). Findings will identify the degree to which *Building Better Caregivers* successfully achieves the Reach, Implementation, and Maintenance domains of RE-AIM for caregivers.

**Data analyses using a subest of intervention caregivers:** We will sample for caregivers (n=60 total) from all US regions (n=15 per region—West, Midwest, South, Northeast) to achieve the expected saturation of themes within 12-15 interviews/region. Using data collected through telephone-based 30 minute interviews we will probe for deeper understanding of the caregiver's impressions of and responses to the workshop. Interviews will be audiorecorded and electronically stored on secure computers. Professionals will transcribe and anonymize recordings. A code key linking transcripts to participants will be kept in a secure electronic file accessible to only the study PI and research coordinator. Data analysis will be conducted concurrently with ongoing data collection to ensure timely generation of findings. Interview transcripts and summary notes will be uploaded into NVivo qualitative data management and analysis software. Using NVivo the coding team will perform thematic analysis of interview transcripts. The coding team will consist of the research coordinator and RA. They will read each transcript and assign codes to identify emergent themes and also apply *a priori* deductive codes derived from the RE-AIM framework. After coding approximately 6-7 transcripts, the coding team will convene with Drs. [name] and [name] (investigators with qualitative research expertise) to compare and discuss individual styles of coding and approaches to achieve coding consistency and begin to identify among emergent codes whether there are relevant sub-codes to be agreed upon. The coding team and investigators will meet for a similar discussion following coding of an additional 6-7 transcripts to assure consistency. After coding is completed, the same group will convene, discuss, and reach consensus on interview themes, qualitative findings, and illustrative quotes.

**8.27 REFERENCES: List only the 5-10 most relevant references (a separate bibliography can be attached for reference purposes if this study involves novel approaches, agents, or an emerging technology that the IRB may not be familiar with):**

## 9.0 Drugs and Devices

**9.1 \* DRUGS AND/OR BIOLOGICS: Are you STUDYING any drugs and/or biologics that are either approved or unapproved: (REQUIRED)**

Yes  No

**9.3 \* MEDICAL DEVICES: Are you STUDYING any medical devices, in vitro diagnostics, or assays that are either approved or unapproved:(REQUIRED)**

Yes  No

## 10.0 Sample Size and Eligibility Criteria

**10.1 ENROLLMENT TARGET: How many people will you enroll:**

If there are multiple participant groups, indicate how many people will be in each group:

**For Aim 1 Sample for RCT.** We will recruit 640 rural dementia caregiver adults through 19 community organizations (serving rural communities in 17 states to implement a randomized, attention controlled clinical trial. 320 in the intervention group and 320 in the control group for a total of n=640.

**For Aim 2 Sample for In-depth Interviews.** We will randomly select a sub-set of intervention group caregivers for semi-structured telephone interviews regarding workshop implementation characteristics. We will sample for caregivers (n=60 total) from all US regions (n=15 per region—West, Midwest, South, Northeast).

**For Aim 1 and Aim 2 Sample for Learning Collaborative.** 19 community organizations (serving rural communities in 17 states) will have at most 2 representatives participating in the Learning Collaborative (n=2\*19=38).

**10.3 SAMPLE SIZE JUSTIFICATION: Explain how and why the number of people was chosen. For multi-site studies, this is referring to the number that will be enrolled across all sites:**

The study is powered on the co-primary outcome with the lowest effect size in pilot studies—the PHQ-8 depression symptoms score (effect size 0.27). We will use a recruitment target of 640 participants. We assume 30% loss to follow-up, thus expecting 448 caregivers (224 per group) will complete the study at 12 months. This sample size of 448 will allow us to detect a PHQ-8 effect size of 0.265 with a power of 0.8 at a significance level of 0.05 (two-sided). The effect size of 0.265 corresponds to a 1.5 difference in PHQ-8 score (range 0-24) between groups assuming a common standard deviation of 5.6. We also will have the power to detect a 1.4 difference in the co-primary outcome of stress score (range 0-10) between the two groups.

If we encounter problems meeting trial enrollment benchmarks, we will work with local organizations and others to find alternative recruitment strategies such as health system-based patient portals or recruitment through national caregiver discussion groups. We also can add additional partner organizations after the start of the study.

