If enough caregivers are enrolled in a 2-week period (e.g., 54) to use a 1:1 randomization, that will be used; if there are somewhat fewer (e.g., 41), 2:1 randomization will be used; if fewer (e.g., 36), 3:1 randomization will be used. Use of this flexible approach has achieved high retention rates in the prior trials (e.g., Lorig KR, Sobel DS, Stewart AL, et al. Evidence suggesting that a chronic disease self-management program can improve health status while reducing hospitalization: a randomized trial. *Medical care* 1999;37:5-14). Assuming that the

randomization with varied ratios will increase the retention rate from 50% to 75% and the randomization ratio will be controlled for as a categorical variable in the analysis model, 480 caregivers at the end of the study will allow us to detect a partial correlation of 0.13 between the treatment and outcome with a power of 0.82 at a significance level of 0.05 (two-sided).

Randomization plan	Total sample size	Retention rate	# participants at the end of the study	Power	Effect size
Original 1:1	640	70%	448	0.80	0.265 (a treatment group difference of 1.5 in PHQ-8 score)
Original 1:1 but with revised downward estimate of retention based on new information from VA	640	50%	320	0.63	0.265
Fixed 2:1	640	75%	480	0.78	0.265
Fixed 3:1	640	75%	480	0.71	0.265
Varying 1:1, 2:1, 3:1	640	75%	480	0.82	A partial correlation of 0.13 between treatment and PHQ-8 score.

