Our team has developed and pilot tested an online 6-week, highly interactive, small-group self-management and skills-building workshop for caregivers of loved ones with dementia or cognitive impairment. The workshop, called Building Better Caregivers, is based on Self-Efficacy Theory boosted by enhanced social support and builds on substantial evidence from other dementia caregiver interventions and self-management programs. Every part of the workshop is designed to enhance caregiver self-management behaviors, dementia caregiving skills, and peer social support. In our evaluations of the program in non-randomized studies, caregivers experienced significant improvements in stress, depression symptoms, and self-efficacy (Cohen's d standardized effect size range 0.27-0.70), and partners experienced improved well-being (effect size = 0.40). Participation by rural dementia caregivers ranged from 30-50%, and the community organizations that partnered with us expressed enthusiasm for expanding the workshop reach to a greater number of rural dementia caregivers.

Building on these encouraging preliminary findings, we now propose to conduct a hybrid effectiveness-implementation randomized controlled trial of the Building Better Caregivers online self-management workshop among rural caregivers of partners with Alzheimer's disease or other forms of dementia. Effectiveness-implementation trials focus a priori on assessing both clinical effectiveness and implementation and can therefore reduce time to translation.

**8.7 \* TREATMENT PROTOCOL: Is this a treatment study, i.e. does this study intend to provide treatment to individuals with a medical or psychological condition: (REQUIRED)**

Yes  No

**8.8 \* BILLABLE PROCEDURES: Does this study involve any services or procedures (e.g. physical exams, surgeries, lab tests, imaging studies, or drugs) that could be billable to patients, their insurance, Sponsor, or any other entity (answer 'Yes' even if the study is going to pay for all the procedures): (REQUIRED)**

Yes  No

If you are not sure if your study involves billable procedures, send an email to the **UCSF Office of Clinical Research (OCR)** for help answering this question.

**8.9 \* COMMON RESEARCH ACTIVITIES: Types of research activities that will be carried out. Check all that apply and describe in more detail in the 'Procedures / Methods' section: (REQUIRED)**

- Interviews, questionnaires, surveys
- Educational or cognitive tests
- Focus groups

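### Is the 1.4-point stress difference in Section 10.3 a wrong detection limit for a co-primary outcome?

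*Combined protocol and SAP*

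**What the plan says.** Section 10.3 of the combined protocol and SAP begins with the choice of outcome for the sample size: "The study is powered on the co-primary outcome with the lowest effect size in pilot studies". That outcome is PHQ-8, with a pilot effect size of 0.27. Of 640 enrolled, 30% are assumed lost, "thus expecting 448 caregivers (224 per group) will complete the study at 12 months". The PHQ-8 result follows: "This sample size of 448 will allow us to detect a PHQ-8 effect size of 0.265 with a power of 0.8", two-sided 0.05, which the section converts to 1.5 points using an SD of 5.6.

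Stress gets one closing sentence: "We also will have the power to detect a 1.4 difference in the co-primary outcome of stress score (range 0-10) between the two groups". Neither document gives an SD, effect size or power level for stress.

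Two other places bear on it. Section 8.12 describes the stress item differently: "We will use a single-item visual numeric scale (range 1-10) developed by our team". Section 8.6 gives one pilot range for stress, depression symptoms and self-efficacy together: "Cohen's d standardized effect size range 0.27-0.70".

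The Protocol document (the August 2019 power explanation) adopts varying allocation ratios and restates power for PHQ-8 only: "480 caregivers at the end of the study will allow us to detect a partial correlation of 0.13 between the treatment and outcome". It gives no stress figure.

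**The concern.** Stress is one of two co-primary outcomes, and 1.4 is the only planning figure it has. The sentence comes straight after a calculation at power 0.8, and its wording invites the reader to carry that 0.8 forward. Read that way, 1.4 is the 80%-power detectable difference for stress, and a raw score on a ten-point scale cannot vary enough for that.

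At stake would be how a stress result is read. If the SD were 2 to 3 (an assumption), the 80%-power limit would be about 0.5 to 0.8 points. Someone who took 1.4 as the limit would think the trial 1.8 to 2.6 times less sensitive than it is, and might dismiss a 0.8-point effect as out of reach. The two scale ranges add doubt: 1.4 is 14% of a 0-10 range (1.4/10) and 15.6% of a 1-10 range (1.4/9).

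**Working it through.** **Inputs.** From Section 10.3: 224 completers per group, two-sided alpha 0.05, power 0.80, PHQ-8 effect size 0.265 and SD 5.6, stress difference 1.4. From Sections 8.12 and 10.3: stress range 1-10 or 0-10. The stress SD is not given, so every SD below is an assumption.

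**1. Reproduce the PHQ-8 figure.** Completers: 640 × 0.70 = 448. Detectable standardised difference: d = (z₀.₉₇₅ + z₀.₈₀) × √(2/224) = 2.8016 × 0.09449 = 0.2647 (0.2653 by the noncentral t). Power at d = 0.265 is 0.801 by the normal formula and 0.799 by the noncentral t. In points, 0.265 × 5.6 = 1.48, stated as 1.5. The plan's figure holds.

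**2. Read 1.4 as the same kind of limit.** Required SD = 1.4/0.2653 = 5.28 (5.29 with 0.2647). The largest SD on a bounded scale is half its range: 5.0 on 0-10 and 4.5 on 1-10. So 1.4 cannot be the 80%-power limit for a raw-score comparison.

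**3. Read 1.4 as a difference the trial has enough power for.** Power ≈ Φ(1.4/(SD × √(2/224)) − 1.96), and the 80% limit is 0.2647 × SD:

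| Assumed SD | 80% limit (points) | Power for 1.4 |
|---|---|---|
| 2.0 | 0.53 | > 0.999 |
| 2.5 | 0.66 | > 0.999 |
| 3.0 | 0.79 | 0.999 |
| 4.0 | 1.06 | 0.959 |
| 4.5 (maximum on 1-10) | 1.19 | 0.909 |
| 5.0 (maximum on 0-10) | 1.32 | 0.842 |

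The limit is below 1.4 in every row, so the sentence is true for any possible raw-score SD on either range.

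**4. Other ways 1.4 could have arisen.** SD implied at 224 per group by the normal formula: 90% power, 4.57; 95% power, 4.11; 80% power at alpha 0.025, 4.81; 90% power at alpha 0.025, 4.21. All fit 0-10. If 1.4 is a pilot difference at the top of the pilot range, the SD is 1.4/0.70 = 2.0; Section 8.6 does not say that 0.70 belongs to stress. The text does not settle which reading was meant.

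**5. The revised design, 480 completers.** Detectable d at 80% power is 0.2563 if all are 1:1 (240/240), 0.2718 at 2:1 (320/160) and 0.2959 at 3:1 (360/120). Multiplied by the maximum SD:

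| Allocation | SD 4.5 | SD 5.0 |
|---|---|---|
| 1:1 | 1.15 | 1.28 |
| 2:1 | 1.22 | 1.36 |
| 3:1 | 1.33 | 1.48 |

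Only one cell exceeds 1.4: every block at 3:1 with half the responses at each end of a 0-10 scale. Power for 1.4 there is 0.76. At SD 4 and 3:1 it is 0.91.

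**6. The scale range.** It enters no formula in either document. The mixed models in Section 8.26 estimate variance from the data, and a between-group difference in points does not depend on whether the lowest answer is labelled 0 or 1.

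**The case for a change.** The best case for a change is this. The sentence states no power of its own, so its wording can only point back to the 0.8 just given, and on that reading 1.4 is impossible without assuming any SD. PHQ-8 has an effect size, an SD and a power, while the other co-primary outcome has none. The 2019 revision did not touch stress, so its one planning figure still belongs to the 448-completer, 1:1 design. The remedy would be a sentence.

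Three parts of this stand: the stress SD and power level are missing, the two ranges disagree, and a reader cannot recompute 1.4.

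The rest is weaker. The sentence never calls 1.4 a minimum and never attaches 0.8 to it. Section 10.3 has already named PHQ-8 as the outcome with the smallest pilot effect, so a closing remark that the easier outcome is also covered is naturally a sufficiency check. The impossibility also applies to raw scores only. The primary test is the group-by-time interaction, which concerns change: with a raw SD of 4.5 and a correlation of about 0.31 between baseline and 12 months, the change SD is √(2 × 4.5² × (1 − 0.31)) ≈ 5.28. A design effect of (1.4/1.19)² ≈ 1.38 for organisations would likewise make 1.4 the limit at SD 4.5. Neither is stated and both are strained, but they show that the ceiling argument does not prove an error.

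Nor is the reader left without a stress target. The standardised limit of 0.265 applies to any continuous outcome under the same formula; only the conversion to points is missing.

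**Conclusion.** The concern does not call for a change. Section 10.3 omits the SD and power behind a secondary remark, and the 0-10 against 1-10 discrepancy is a clerical slip. No stated figure is shown to be wrong.

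As a sufficiency claim the sentence holds. At 224 per group, power for 1.4 points is at least about 0.84 at any possible raw-score SD, and about 0.999 or more at assumed SDs of 2 to 3. Under the 480-completer plan it stays above 0.80 except when allocation is almost entirely 3:1 and the SD is close to its ceiling on 0-10 (0.76 at the extreme).

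This rests on the two-sample comparison of raw scores that reproduces the document's own PHQ-8 figure, with no design effect and no change-score variance.

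Writing in an SD would make the remark checkable, but the documents do not supply one. Doing so would leave the sample size (set by PHQ-8), alpha, the mixed-model analysis and the reading of the results as they are. The analyst will estimate the stress effect and its confidence interval from the observed data, on whichever range the fielded item uses.
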